1.1 Background and Rationale

Skin aging is a multifactorial biological process influenced by intrinsic physiological changes (chronological aging, hormonal decline, genetic factors) and extrinsic environmental factors (UV exposure, pollution, lifestyle). Collagen is a key structural protein in the dermis, essential for maintaining elasticity and integrity. Oral supplementation with specific bioactive collagen peptides (SCP) has been proposed as a non-invasive intervention to support dermal structure, hydration, and wrinkle reduction.

1.2 Study Objectives

- **Primary Objective:** Evaluate the effect of 8-week oral SCP supplementation on stratum corneum hydration (SCH) in healthy adult women.
- **Secondary Objectives:** Assess effects on transepidermal water loss (TEWL), skin elasticity (R2, R5), skin firmness (F4), collagen content (2 mm depth), periorbital wrinkle morphology (area, volume, depth), and subjective skin assessment.

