1.3 Study Design

- Type: Single-center, prospective, randomized, double-blind, placebo-controlled clinical trial
- Duration: 8 weeks
- Visits: Baseline (Week 0), Week 4, Week 8
- Intervention: 2.5 g SCP (VERISOL®) daily or matching placebo
- Randomization: 1:1 ratio, computer-generated list, blinding maintained for participants and investigators

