1.4 Study Population

- **Sample Size:** 66
- **Inclusion Criteria:** Healthy women aged 35–55, Fitzpatrick skin type III–IV, specific grading of crow's feet and under-eye fine lines
- **Exclusion Criteria:** Recent use of anti-inflammatory medication, pregnancy/lactation, dermatologic conditions, recent aesthetic procedures, systemic diseases affecting skin, allergy to study product

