1.7 Statistical Analysis

- Repeated-measures ANOVA for primary and secondary endpoints
- Baseline comparisons: independent-samples t-tests or Mann–Whitney U tests as appropriate
- Within-group analyses: repeated-measures ANOVA with Bonferroni correction
- Rank transformation applied for non-normal endpoints
- Effect size: partial eta-squared (η^2) thresholds of 0.01 (small), 0.06 (medium), 0.14 (large)
- Significance: two-sided, $p < 0.05$

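### The stated primary method, a repeated-measures ANOVA over weeks 0, 4 and 8, does not isolate the SCP-placebo difference at week 8 that the primary objective points to

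*Protocol*

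**What the plan says.** Protocol section 1.2 sets one primary objective: "Evaluate the effect of 8-week oral SCP supplementation on stratum corneum hydration (SCH) in healthy adult women". Section 1.3 describes a placebo-controlled comparison with "Visits: Baseline (Week 0), Week 4, Week 8" and "Randomization: 1:1 ratio, computer-generated list"; section 1.4 gives "Sample Size: 66".

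Section 1.7 names one method for this objective: "Repeated-measures ANOVA for primary and secondary endpoints". A separate line covers changes inside each arm: "Within-group analyses: repeated-measures ANOVA with Bonferroni correction". Because that line stands apart, the first is best read as the between-arm model, and the Bonferroni correction belongs to the within-arm work only. The significance level is a general line, "Significance: two-sided, $p < 0.05", which also serves the baseline t-tests and Mann-Whitney tests.

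The protocol gives no expected difference in SCH, no SD and no between-visit correlation. The only effect sizes are generic partial eta-squared "thresholds of 0.01 (small), 0.06 (medium), 0.14 (large").

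**The concern.** The effect of an 8-week course is most naturally the difference between SCP and placebo at its end, which is also the last visit. A two-arm, three-visit repeated-measures ANOVA yields three F tests, and none is that difference:

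- **Time** pools both arms and carries no information about SCP against placebo.
- **Group** averages the arm difference over all three visits, including week 0, before any product is taken.
- **Group-by-time** has 2 numerator degrees of freedom. It asks whether the arm difference varies over the visits in any way. It does not single out week 8 and has no direction.

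Two things are at stake. A significant primary result might not mean that SCP and placebo differ after 8 weeks. And if the benefit does build up to week 8, the stated test spreads its sensitivity over patterns nobody is asking about, in a trial of only 66 women.

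**Working it through.** **Inputs from the protocol.** 66 women at 1:1, so n = 33 per arm; three visits; two-sided 0.05. The protocol states no power or effect figure for SCH, so there is none to reproduce.

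**Assumptions (not in the protocol).** Normal data, SD 1 at each visit, equal correlation ρ between visits, no dropout. The effects are illustrative and ρ is varied over 0.3, 0.5 and 0.7.

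**Interaction test.** Let d be the SCP-placebo differences at weeks 0, 4 and 8, and c the deviations of d from their own mean. The noncentrality is λ = (n/2) × Σc² / (1 − ρ), with 2 and 2 × 64 = 128 degrees of freedom and a critical F of 3.07.

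*Difference at week 4 only, d = (0, 0.5, 0).* The mean is 0.1667 and c = (−0.1667, 0.3333, −0.1667), so Σc² = 0.1667 and λ = 16.5 × 0.1667 / (1 − ρ) = 2.75 / (1 − ρ).

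| ρ | λ | Group-by-time significant | Week-8 contrast significant |
|---|---|---|---|
| 0.3 | 3.93 | 40% | 5% |
| 0.5 | 5.50 | 53% | 5% |
| 0.7 | 9.17 | 77% | 5% |

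The week-8 contrast stays at 5% because no week-8 difference exists.

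Σc² is also 0.1667 for d = (0, 0, 0.5) and for d = (0, 0.5, 0.5). The interaction test therefore has identical power for an effect at week 4 only, at week 8 only, or at both. It cannot tell the pattern that answers the objective from the one that does not.

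*Benefit that builds, d = (0, 0.25, 0.5).* Here c = (−0.25, 0, 0.25), Σc² = 0.125 and λ = 2.0625 / (1 − ρ).

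**Baseline-adjusted week-8 comparison (ANCOVA).** SE = √[(1 − ρ²) × 2/33], with 63 degrees of freedom. At ρ = 0.5, SE = √(0.75 × 0.0606) = 0.213 and 0.5 / 0.213 = 2.35. This SE omits a very small allowance for chance baseline imbalance, so the ANCOVA column below comes from simulation.

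| ρ | λ, interaction | Power, interaction | Power, week-8 ANCOVA |
|---|---|---|---|
| 0.3 | 2.95 | 0.31 | 0.55 |
| 0.5 | 4.13 | 0.42 | 0.63 |
| 0.7 | 6.88 | 0.64 | 0.80 |

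**Cross-check.** Simulating 20,000 trials per setting reproduced the formula results for the interaction to within about 0.01. With no treatment effect, the interaction was significant in 4.8% to 5.2% of trials.

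**Where the gain is smaller.** With 0.5 SD at both week 4 and week 8, simulated power is 0.40 / 0.54 / 0.76 for the interaction and 0.55 / 0.64 / 0.79 for week-8 ANCOVA at ρ = 0.3 / 0.5 / 0.7. The two nearly meet at high correlation.

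**The case against.** **The SAP may name the deciding term.** It may, and a bare silence on that detail would be no finding. But the protocol has already chosen the primary method, and the point is about that choice: even with group-by-time named as decisive, the test does not target week 8.

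**The 8 weeks may describe only the length of the course.** This is a fair reading; the objective does not literally say at week 8. A group-by-time test over weeks 0, 4 and 8 is a recognised way to study such a course, and no two sections contradict each other. So this is a mismatch between target and test, not an outright error.

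**A week-4-only difference is a real effect of SCP.** This stands. A significant interaction in that case is a true effect at a time point other than the natural target. It is not a false positive.

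**The week-4-only pattern is a constructed case.** Nothing in the protocol suggests an effect that vanishes under continued daily use. With smaller week-4 differences the figure falls: at ρ = 0.5 it is 22% for 0.3 SD and 12% for 0.2 SD. The power comparison does not depend on this pattern.

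**Stronger readings.** A reader might infer that any of the three F tests, including a shared change over time in both arms, may count as success, and hence that type I error is inflated. The protocol does not say so. It contains no success rule, the design is placebo-controlled, the significance level is a general line rather than a rule attached to the whole ANOVA, and within-arm analyses are listed apart. If group-by-time decides, type I error under no effect is 5%.

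**Conclusion.** The concern holds as a mismatch between the primary objective and the stated primary method. On the most favourable reading of section 1.7, the deciding test can be significant with no difference at week 8: about 40% to 77% of trials for an assumed 0.5 SD difference at week 4 only, against 5% for a week-8 contrast. It also gives up power when benefit accumulates: 0.31 / 0.42 / 0.64 against 0.55 / 0.63 / 0.80 at correlations 0.3 / 0.5 / 0.7.

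These sizes rest on 33 completers per arm, equal correlation between visits and effect sizes that the protocol does not supply. That the ANOVA terms do not isolate week 8 rests on none of them. The documents do not support a claim of inflated type I error or of success by several routes. The change should be made because it is a cheap improvement; the plan is not invalid without it.

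**What to change.** In section 1.7, state that the single primary test is the baseline-adjusted SCP-placebo difference in SCH at week 8 (ANCOVA, or the equivalent contrast from a longitudinal model), two-sided at 0.05 and reported with its 95% CI. State that week 4 and the repeated-measures ANOVA terms are secondary or supportive. Carry the same wording into the SAP.

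The cost is a sentence or two. It needs no new visits, measurements or participants, because SCH at weeks 0 and 8 is already planned. The small downside is that an effect seen only at week 4 no longer counts as success on the primary objective. The change should be made and dated before unblinding.

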1.3 Study Design

- Type: Single-center, prospective, randomized, double-blind, placebo-controlled clinical trial
- Duration: 8 weeks
- Visits: Baseline (Week 0), Week 4, Week 8
- Intervention: 2.5 g SCP (VERISOL®) daily or matching placebo
- Randomization: 1:1 ratio, computer-generated list, blinding maintained for participants and investigators

1.4 Study Population

- **Sample Size:** 66
- **Inclusion Criteria:** Healthy women aged 35–55, Fitzpatrick skin type III–IV, specific grading of crow's feet and under-eye fine lines
- **Exclusion Criteria:** Recent use of anti-inflammatory medication, pregnancy/lactation, dermatologic conditions, recent aesthetic procedures, systemic diseases affecting skin, allergy to study product

1.5 Study Procedures

- **Physiological Measurements:** SCH, TEWL, skin elasticity (R2, R5), firmness (F4), collagen content (SIAscope)
- **Wrinkle Morphology:** 3D imaging (Derma TOP) and standardized facial imaging (VISIA-CR)
- **Subjective Assessment:** Visual Analogue Scale (VAS) for skin texture, glossiness, smoothness, elasticity, and wrinkle appearance
- **Safety Monitoring:** Recording of adverse events, participant self-reporting, and clinical observation
-

1.6 Study Product

- **Treatment:** VERISOL®, SCP derived from bovine type I collagen, 2.5 g/day
- **Placebo:** Maltodextrin, matched for appearance, taste, and texture
- **Administration:** Dissolved in warm water once daily

1.7 Statistical Analysis

- Repeated-measures ANOVA for primary and secondary endpoints
- Baseline comparisons: independent-samples t-tests or Mann–Whitney U tests as appropriate
- Within-group analyses: repeated-measures ANOVA with Bonferroni correction
- Rank transformation applied for non-normal endpoints
- Effect size: partial eta-squared (η^2) thresholds of 0.01 (small), 0.06 (medium), 0.14 (large)
- Significance: two-sided, $p < 0.05$

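### The repeated-measures ANOVA names no baseline covariate and no term that tests treatment; adjusting for baseline, with one week-8 primary contrast, is usually more efficient and costs almost nothing

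*Protocol*

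**What the plan says.** Section 1.7 gives one line on the main analysis: "Repeated-measures ANOVA for primary and secondary endpoints". No covariate is listed, and neither the group main effect nor the group-by-time interaction is named as the treatment test.

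Baseline is mentioned in section 1.7 only for a between-arm check: "Baseline comparisons: independent-samples t-tests or Mann–Whitney U tests as appropriate". A separate line reads "Within-group analyses: repeated-measures ANOVA with Bonferroni correction".

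Section 1.3 sets the schedule: "Visits: Baseline (Week 0), Week 4, Week 8". It does not say which visits are levels in the model. The other relevant inputs are "Randomization: 1:1 ratio, computer-generated list" (section 1.3), "Sample Size: 66" (section 1.4) and "Significance: two-sided, $p < 0.05" (section 1.7). The primary objective in section 1.2 concerns the effect of eight weeks of supplementation on SCH.

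**The concern.** In a randomised trial the true difference between arms at week 0 is zero, so the week-0 value is useful mainly as a predictor of later readings. A repeated-measures ANOVA without a covariate leaves three possible roles for it, and none is usually the best:

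- **Group main effect over weeks 0, 4 and 8.** The known zero is averaged into the estimate.
- **Group-by-time over the three visits.** Week 0 is the reference, so baseline is used. But each woman's full baseline value is subtracted instead of a regression-weighted part of it, and the signal is spread over two degrees of freedom.
- **Weeks 4 and 8 only.** Baseline plays no part in the treatment comparison.

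The t-tests or Mann–Whitney tests at baseline do not help. They ask whether randomisation produced a difference by chance and leave the treatment estimate unchanged. The stake is precision on the primary and every continuous secondary endpoint, in a trial of 66 women whose protocol states no power. The choice of term also matters in itself: on the same data, the main effect and the interaction can differ widely in power.

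**Working it through.** **The plan's own figure.** The total of 66 cannot be reproduced, because the protocol gives no target difference, SD, power or dropout. For orientation, 33 per arm gives about 80% power for an unadjusted comparison at 0.69 SD (normal approximation), so a week-8 difference near 0.70 SD is a reasonable illustration.

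**Inputs.** From the protocol: n = 33 per arm (66 at 1:1), two-sided 0.05, visits at weeks 0, 4 and 8. Assumed: SD 1 at each visit, equal correlation ρ between visits, and differences of 0/0.35/0.70 SD (gradual) or 0/0.70/0.70 SD (complete by week 4).

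**Is week 0 a level?** The within-group repeated-measures analysis carries a Bonferroni correction. With weeks 4 and 8 alone there is one visit contrast and nothing to correct across visits. Together with the three-visit schedule, this makes week 0 a likely level, though no sentence says so.

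**Dilution of the main effect.** Gradual: (0 + 0.35 + 0.70)/3 = 0.35 SD, half the week-8 difference. Complete by week 4: (0 + 0.70 + 0.70)/3 = 0.47 SD, two thirds of it.

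**Noncentrality λ, with n/2 = 16.5; gradual effect, ρ = 0.5**

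- Group main effect: 16.5 × 0.35² / ((1 + 2ρ)/3) = 3.03, df 1, 64
- Group-by-time: 16.5 × Σ(dₜ − mean d)² / (1 − ρ) = 16.5 × 0.245 / 0.5 = 8.09, df 2, 128
- Week-8 change score: 16.5 × 0.70² / (2(1 − ρ)) = 8.09, df 1, 64
- Week-8 ANCOVA on baseline: 16.5 × 0.70² / (1 − ρ²) = 8.085 / 0.75 = 10.78, df 1, 63

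Power (%) from the noncentral F distribution:

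| Effect | ρ | Main effect | Interaction | Change score, week 8 | ANCOVA, week 8 |
|---|---|---|---|---|---|
| Gradual | 0.5 | 40.3 | 71.2 | 80.0 | 89.8 |
| Gradual | 0.7 | 34.7 | 91.2 | 95.1 | 97.5 |
| Gradual | 0.8 | 32.5 | 98.4 | 99.3 | 99.7 |
| Complete by week 4 | 0.5 | 62.8 | 83.6 | 80.0 | 89.8 |
| Complete by week 4 | 0.7 | 55.1 | 97.1 | 95.1 | 97.5 |
| Complete by week 4 | 0.8 | 51.8 | 99.8 | 99.3 | 99.7 |

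If week 0 is left out, an unadjusted week-8 comparison has λ = 16.5 × 0.49 = 8.09 and 80% power at every ρ.

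**Where the gap comes from.** For the gradual effect at ρ = 0.5, interaction to ANCOVA is 89.8 − 71.2 = 18.6 points. Of these, 80.0 − 71.2 = 8.8 come from testing one contrast instead of a 2-df omnibus, and 89.8 − 80.0 = 9.8 from the covariate. At ρ = 0.7 the covariate adds 97.5 − 95.1 = 2.4 points.

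**Smaller effect (0.50 SD at week 8), ρ = 0.3 / 0.5 / 0.7 / 0.8.** Gradual: interaction 31 / 42 / 64 / 82%, ANCOVA 55 / 64 / 80 / 92%. Complete by week 4: interaction 40 / 54 / 77 / 92%, with the same ANCOVA figures.

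**Chance imbalance.** The baseline difference has standard error √(2/33) = 0.246 SD, so an imbalance beyond 0.25 SD in either direction occurs in about 31% of trials. Given such an imbalance, the change-based estimate shifts by (1 − ρ) × 0.25: 0.125 SD at ρ = 0.5 and 0.05 SD at ρ = 0.8. The ANCOVA estimate does not shift in expectation.

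**Type I error.** Simulation of 20,000 trials with no effect at ρ = 0.5 rejected in 5.0% (main effect), 5.3% (interaction) and 5.1% (ANCOVA).

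**The case against.** Section 1.7 is a summary. Model terms and covariates are commonly left to a statistical analysis plan, and that plan is not shown. This stands as far as missing detail goes: the unnamed term alone would not be a finding. But the method itself is chosen in the protocol, and an analysis plan that used ANCOVA instead would depart from it.

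A reader might infer more than the documents support:

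- **That baseline data dilute the treatment effect.** This is true only of the group main effect, and the protocol does not say that this is the test. With week 0 as a level, group-by-time is the natural treatment test and is not diluted. That week 0 is a level is itself inferred, from a line about within-group analyses.
- **That power is lost for no benefit.** The interaction removes between-woman variation. At ρ = 0.7 it has 91% or 97% power, against 80% for an unadjusted week-8 comparison.
- **That the loss must be large because women differ far more than they change.** That premise implies high ρ, where the interaction's loss is small. It also makes the main effect look worse.
- **That the analysis is invalid.** Type I error holds, and the change-based estimate is unbiased over randomisation. The shift arises only conditional on the imbalance observed.

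Nor is the whole gap due to the missing covariate, since about half of it at ρ = 0.5 comes from the 2-df test.

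**Conclusion.** The point holds as a matter of efficiency. On each reading of section 1.7, baseline adjustment with one named contrast is generally at least as efficient as the stated method. The size depends on the reading:

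- **Main effect over three visits:** a serious loss, 40% against 90% power at ρ = 0.5 and 35% against 98% at ρ = 0.7 (gradual effect).
- **Group-by-time:** about 19 points at ρ = 0.5, 6 at 0.7 and 1 at 0.8 with a gradual effect. With an effect complete by week 4, about 6 points at ρ = 0.5 and practically none from 0.7 upwards.
- **Week 0 excluded:** an unadjusted week-8 test has 80% power, against 90% or more with adjustment at ρ of 0.5 or higher.

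These figures rest on assumed differences, equal variances and equal correlations; the protocol supplies none of them. This is a free improvement that is recommended, not a correction without which the trial's conclusions would be unsound.

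**What to change.** In section 1.7, for SCH and each continuous secondary endpoint, replace the repeated-measures ANOVA with a model that has:

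- weeks 4 and 8 as the outcomes;
- fixed effects for treatment, visit and treatment-by-visit;
- the endpoint's own baseline value and baseline-by-visit as covariates.

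Name the adjusted SCP–placebo difference in SCH at week 8, with its 95% confidence interval, as the single primary contrast. Without that step, a model with treatment-by-visit would again leave open which visit or average tests treatment. Describe baseline by arm and drop the significance tests there.

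The cost is a change of wording in the protocol and in any analysis plan, plus one or two degrees of freedom. The week-0 visit is already scheduled, so no new data, visits or participants are needed.

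### Repeated-measures ANOVA over weeks 0, 4 and 8, run without imputation, would leave out any woman who misses a visit; a baseline-adjusted mixed model with a week-8 contrast is a cheap improvement

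*Protocol*

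**What the plan says.** Protocol section 1.7 names one method for the primary and secondary endpoints: "Repeated-measures ANOVA for primary and secondary endpoints". The same section adds "Effect size: partial eta-squared (η^2) thresholds of 0.01 (small), 0.06 (medium), 0.14 (large", a measure built from ANOVA sums of squares, and "Significance: two-sided, $p < 0.05".

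Section 1.3 gives the levels of the repeated factor: "Visits: Baseline (Week 0), Week 4, Week 8". Section 1.2 states the primary objective: "Evaluate the effect of 8-week oral SCP supplementation on stratum corneum hydration (SCH) in healthy adult women". Section 1.4 gives the size ("Sample Size: 66") and section 1.3 the allocation ("Randomization: 1:1 ratio, computer-generated list"), so 33 women per arm.

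The protocol names no mixed or likelihood-based model. It does not use the word classical and states no completers rule. That all three visits enter the primary model, and that week 8 is the contrast of interest, is implied by the visit list and the objective but not written down.

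**The concern.** Partial eta-squared points to the sums-of-squares form of the analysis. That form needs a full row of three values for each woman. Run on unimputed data, it has two consequences:

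- A woman with baseline and week-8 hydration but no week-4 value drops out of the 8-week comparison, although both values that bear on that comparison were measured.
- A woman who leaves after week 4 contributes nothing, although her week-4 value helps predict where she would have been at week 8.

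In a trial of 66 women, discarding measured week-8 values wastes information. If leaving is related to how the skin responded by week 4, the women who remain are a selected group, and the SCP-placebo difference can shift in either direction depending on which arm loses its poor responders.

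**Working it through.** **Inputs.** From the protocol: 66 women, 1:1, visits at weeks 0, 4 and 8. The protocol gives no dropout rate, visit correlation or expected effect, so those below are assumptions, varied over a range. For the same reason the figure of 66 cannot be reproduced; nothing here depends on how it was reached.

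**1. Does one missing value matter to the method?** A data set of 66 women with three visits (198 values) was built and one week-4 value deleted. A classical repeated-measures ANOVA routine rejected the data as unbalanced, so the woman must be dropped (leaving 65) or her value imputed. A mixed model kept all 66 women and 197 values.

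**2. How many women are affected?** If a fraction m misses each post-baseline visit independently, the expected number without a full record is 66 × (1 − (1 − m)²):

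| m | Women without all three visits |
|---|---|
| 2% | 2.6 |
| 5% | 6.4 |
| 10% | 12.5 |

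**3. Precision, visits missed completely at random.** At m = 10%:

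- complete on all visits: 66 × 0.9 × 0.9 = 53.5
- with a week-8 value: 66 × 0.9 = 59.4
- ratio of standard errors: √(0.9 / 0.81) = 1.054, about 5% larger

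There is no bias here: a simulation with a true difference of 0.70 SD returned 0.70 from complete cases.

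**4. Bias, dropout following week-4 response.** Large simulated arms, equal correlation ρ between visits (0.5 to 0.7), true week-8 difference 0.50 SD. Half of the women whose change at week 4 lies in the lowest third for placebo leave before week 8. The complete-case estimate is the difference in mean change from week 0 to week 8.

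| Scenario | Complete-case estimate (SD) | Bias |
|---|---|---|
| Placebo only, 17% of that arm leaves | 0.39-0.42 | about 17-22% |
| Same rule in both arms | 0.46-0.49 | about 3-8% |
| Placebo only, 5% of that arm leaves | 0.47-0.48 | about 4-6% |

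The bias column is (0.50 − estimate) / 0.50; for example (0.50 − 0.40) / 0.50 = 20%. In the 17% scenario, an estimate that also uses baseline and week 4, under missing at random, returns about 0.50.

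A second set-up, with a true difference of 0.70 SD, ρ = 0.6 and dropout probability falling smoothly with week-4 change, gave the same picture. With a shared mechanism, complete cases gave 0.67-0.68. With response-related dropout in placebo only, they gave 0.67, 0.64 and 0.59 at overall dropout of about 5%, 10% and 20%. The estimate using all available data stayed at 0.70.

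**5. How much of the gap is due to dropping women?** In the 17% scenario, a baseline-adjusted analysis of completers alone gives 0.44-0.45. At ρ = 0.5 this recovers about (0.44 − 0.39) / (0.50 − 0.39) = 0.05 / 0.11, a little under half of the gap. Baseline adjustment therefore repairs part of the bias, and using the week-4 data repairs the rest.

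**The case against.** The strongest objection is that listwise deletion is not inherent in the protocol's words. Repeated-measures ANOVA on imputed data keeps all 66 women, and a statistical analysis plan that is not at hand may impute or may fit the model as a mixed model. This stands. The point is conditional on the usual form run without imputation, and the absence of a missing-data rule is not the complaint. What remains is that the protocol's wording and its effect-size measure lead naturally to a method that needs repair before it can use every measured value, when an equally standard method needs none.

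A reader might infer that the protocol prescribes a completers analysis and that its primary result will be about 20% wrong. The documents support neither. No completers rule is written, and the 20% needs response-related dropout of 17% confined to one arm. Sections 1.3 and 1.6 describe blinding and a matched placebo, which make such a one-sided mechanism less plausible. With a shared mechanism or low dropout the bias is a few per cent, and part of the gap reflects baseline adjustment.

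A reader might also add that the ANOVA assumes sphericity and so inflates the type I error. An uncorrected interaction test does reach about 7% under correlations of 0.3, 0.3 and 0.9. Under a milder pattern (0.6, 0.5, 0.7) it is about 5.1-5.6%, and the Greenhouse-Geisser correction brings the extreme case back to about 5.1%. The protocol does not exclude such a correction, so sphericity does not stand as a separate claim.

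**Conclusion.** The concern holds in conditional form, as an improvement to the method that section 1.7 fixes and not as an error or contradiction in the protocol. If the named ANOVA is run in its usual form on unimputed data, it loses every woman with a missed visit. The price is precision alone when visits are missed completely at random (about 5% on the standard error at an assumed 10% per visit). It is bias when dropout follows response: about 3-8% in the milder scenarios and up to about 20% in a one-sided one. If SCP non-responders are the ones who leave, the direction reverses.

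These sizes rest on assumed dropout rates, visit correlations of 0.5-0.7 and missingness explained by observed values. An 8-week trial may lose few women, and then the effect is small. The change is still worth making because it is cheap and aligns the primary contrast with the 8-week objective in section 1.2.

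**What to change.** In section 1.7, and in the statistical analysis plan if there is one, replace the primary analysis by a baseline-adjusted mixed model for repeated measures:

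- outcome: hydration at weeks 4 and 8, with baseline hydration as covariate
- treatment, visit and their interaction as fixed effects
- unstructured covariance and Kenward-Roger degrees of freedom
- all randomised women with at least one post-baseline value, analysed as randomised
- the treatment contrast at week 8 as the primary test

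Keep repeated-measures ANOVA on completers as a sensitivity analysis. The unstructured covariance also removes the sphericity assumption.

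**Cost.** Wording only: no added participants, visits or measurements, and the procedure is standard.

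**Downside.** Partial eta-squared no longer comes directly from the primary model, so the adjusted mean difference with its confidence interval becomes the main effect measure. Partial eta-squared can still be reported from the sensitivity analysis.

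**Limits.** The model is valid under missing at random. It does not protect against dropout that depends on unobserved values, and it does not recover women with no post-baseline measurement.

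### One p<0.05 threshold covers 9 to 13 secondary endpoints, the only multiplicity correction sits on the within-group analyses, and no rule limits secondary claims if hydration is null

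*Protocol*

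**What the plan says.** Section 1.2 names one primary objective: "Evaluate the effect of 8-week oral SCP supplementation on stratum corneum hydration (SCH) in healthy adult women". The secondary objectives there cover "transepidermal water loss (TEWL), skin elasticity (R2, R5), skin firmness (F4), collagen content (2 mm depth), periorbital wrinkle morphology (area, volume, depth"), which makes eight instrumental outcomes, and then a subjective skin assessment. Section 1.5 describes that assessment as a "Visual Analogue Scale (VAS) for skin texture, glossiness, smoothness, elasticity, and wrinkle appearance", which is five attributes.

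Section 1.7 gives one method for all of these: "Repeated-measures ANOVA for primary and secondary endpoints". The significance level follows as a separate line, "Significance: two-sided, $p < 0.05", and is not limited to the primary. The only adjustment for multiple testing is in this line: "Within-group analyses: repeated-measures ANOVA with Bonferroni correction". The family over which that Bonferroni correction runs is not defined.

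The protocol does not rank the secondary endpoints, make them conditional on the primary or call them exploratory. It also does not name the term of the ANOVA that carries the treatment comparison.

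**The concern.** The protocol makes one explicit decision about multiplicity and attaches it to comparisons inside an arm. Change within an arm mixes any product effect with time, season, regression to the mean and placebo response, so it does not estimate the randomised effect. The between-group tests, which do estimate it, share an unrestricted 0.05 level.

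At stake is what the trial may conclude if SCH shows no difference. Followed as written, Section 1.7 allows whichever of barrier function, elasticity, firmness, collagen, wrinkle morphology or self-assessment falls below 0.05 to be declared significant, and no rule limits how that is read. The rationale in Section 1.1 names dermal structure and wrinkle reduction alongside hydration, so these outcomes are likely to be read as evidence of benefit.

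**Working it through.** The protocol states no familywise error rate, so there is no figure of its own to reproduce.

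**Inputs**
- Level per test: two-sided 0.05 (Section 1.7), so 0.025 in the favourable direction.
- Instrumental secondaries (Section 1.2): TEWL, R2, R5, F4, collagen content, wrinkle area, wrinkle volume and wrinkle depth, so 8.
- VAS (Section 1.5): five attributes. Tested singly, 8 + 5 = 13. As one composite, 8 + 1 = 9. The protocol does not say which, so both are carried.
- Tests per endpoint: one. The visits are "Visits: Baseline (Week 0), Week 4, Week 8", but a repeated-measures ANOVA takes them together in one model.
- Correlation between endpoints: not given. Assumed equal for all pairs, from 0 to 0.7.
- Each endpoint's treatment test is treated as one signed, normally distributed statistic (assumption).

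**Independent tests, product without any effect**
- Either direction: 1 − 0.95^13 = 0.487 and 1 − 0.95^9 = 0.370.
- Favourable direction only: 1 − 0.975^13 = 0.281 and 1 − 0.975^9 = 0.204.

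**Correlated tests** (equicorrelated normal statistics, critical value 1.96)

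| Tests | Correlation | At least one false benefit | At least one false positive, either direction |
|---|---|---|---|
| 13 | 0 | 28% | 49% |
| 13 | 0.5 | 17% | 33% |
| 13 | 0.7 | 12% | 24% |
| 9 | 0 | 20% | 37% |
| 9 | 0.5 | 13% | 27% |
| 9 | 0.7 | 10% | 20% |

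A block pattern for 13 tests (0.6 to 0.8 within outcome families, 0.1 to 0.2 between them) gives 18–22% for a false benefit and 35–41% in either direction, inside the same range. The reference for a single test is 2.5% favourable and 5% in either direction.

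**Expected counts with 13 tests:** 13 × 0.025 = 0.325 false benefits; 13 × 0.05 = 0.65 false positives in either direction.

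**Effect of making claims conditional on the primary.** If SCH is also null, a secondary efficacy claim first needs a false-positive primary, so its probability is at most 5%, whatever the number of secondaries or their correlation.

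**Cost of Holm on top.** The first step over 13 tests is 0.05/13 = 0.0038. With 66 women randomised 1:1, 33 per arm, no dropout and a two-sample t-test as an approximation, power at a standardised difference of 0.70 falls from 80% to 44%. The difference detectable with 80% power rises from 0.70 to 0.95.

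**The case against.** The strongest objection is that multiplicity among secondary endpoints is commonly left to the SAP, which is not shown. Silence on it in a protocol would be no fault, and a general significance level is compatible with a later hierarchy or an exploratory label. That stands as far as silence goes. But Section 1.7 is not silent: it fixes one threshold for everything and puts its one correction on the within-group analyses. A SAP that restricted secondary claims would have to narrow that text.

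Several stronger readings are tempting, and the document does not support them.

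- *A reader might infer that a null product has about a one-in-two chance of showing a benefit.* The 49% counts results in either direction, including the product looking worse than placebo, and assumes independence. For a benefit the figure is 28% at most with 13 tests, and lower with correlation.
- *A reader might take 13 tests as fixed.* Section 1.2 lists subjective assessment as one objective and Section 1.5 lists the VAS attributes as a procedure. Separate testing is an inference.
- *A reader might double the count because there are two post-baseline visits.* Section 1.7 specifies no separate between-group tests at Week 4 and Week 8.
- *A reader might conclude that the within-group Bonferroni is misplaced and should go.* Correcting within-arm comparisons is ordinary and takes no protection from the between-group tests. Dropping it brings no gain and would make before–after claims easier.
- *A reader might infer that the primary conclusion is compromised.* There is one primary endpoint, and the secondary tests do not inflate its error rate.

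**Conclusion.** The point holds in a limited form. As written, Section 1.7 lets any of 9 to 13 secondary endpoints be declared significant at two-sided 0.05 even when SCH is null, and its only correction applies to analyses that do not carry the randomised comparison. With no product effect, the chance of at least one false secondary benefit is about 12–28% for 13 tests or 10–20% for 9, against 2.5% for a single test. The range rests on assumed correlations from 0.7 down to 0 and on one treatment test per endpoint. Higher correlation would lower it further (about 7% at 0.9 with 13 tests).

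The error rate of the primary test is intact. This should be corrected because it changes what the trial may conclude and the correction needs no new data; it does not invalidate the design.

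**What to change.** Add to Section 1.7 a statement along these lines: *Secondary endpoints are supportive. An efficacy claim on a between-group secondary result is made only if the primary between-group test of SCH is significant at two-sided 0.05. Otherwise secondary results are reported as between-group estimates with nominal 95% confidence intervals and support no efficacy claim.* For this to work, the section must also name the ANOVA term or contrast that is the primary between-group test.

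Keep the Bonferroni correction for the within-group analyses, and state that within-group results are not evidence of a product effect.

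Holm's procedure across the secondaries is optional. It is worth adding only if confirmatory claims on individual secondaries are wanted, because conditioning on the primary does not control error among the secondaries once SCH is significant. Its price is the power loss shown in the working.

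The change takes a few sentences and needs no added participants or measurements. Its real cost is that a null primary bars every secondary efficacy claim, including one on an outcome the product truly improves.
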